Participants. A total of 120 families (240 participants) (40 in each treatment condition) children and adolescents (aged 7 - 18 years) along with their parents will participate in the current study. The PADC typically evaluates more than 350 patients per year, approximately one-third of which continue into the treatment program. Thus, we anticipate a recruitment period of approximately twelve months in order to reach our goal of enrolling 240 participants in the study. To determine the degree to which the current study sample reflects the population of patients seen in the PADC, the clinical assessment data will be compared to patients not enrolled in the study, but for whom Research Authorization is available.

To be included, participants must a) be age 7 to 17, or 18 if still in high school and living at home; b) have a DSM-5 anxiety disorder diagnosis, including generalized anxiety disorder, obsessive compulsive disorder, panic disorder, agoraphobia, separation anxiety disorder, social and specific phobias, as assessed on the relevant modules of the (MINI-Kids; (Sheehan et al., 2010) by study staff in the PADC, c) be appropriate for the PADC standard weekly outpatient therapy program, d) be interested in starting outpatient therapy, e) have the anxiety disorder as their primary diagnosis, f) if taking a selective serotonin reuptake inhibitor, SNRI, tricyclic, or antipsychotic medication, agree to no changes during the 14 weeks of the study (medication status will be recorded from interview and using review of the electronic medical record).

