Patients will be excluded from the study if they meet any of the following criteria: (a) history of and/or current psychosis, autism, bipolar disorder, or current suicidality, or eating disorder as assessed during the initial clinical interview and all available clinical information; (b) current positive diagnosis in the child's caregiver of mental retardation, psychosis, or other psychiatric disorders or conditions that would limit his/her ability to understand CBT and follow-through with treatment directives (based on clinical interview); (c) secondary diagnosis of oppositional defiant disorder or major depression of sufficient severity to prevent anxiety treatment, (d) severity of symptoms that warrant higher level of care (i.e. intensive, residential, IOP, inpatient), (e) family is unable to attend weekly sessions (i.e. geographical or scheduling barriers), of (f) history of good quality exposure or CBT.

Procedures

See Figure 1. Participants who have contacted or been referred to the PADC for evaluation and treatment of an anxiety disorder will complete the standard clinical intake procedure for the PADC. Families whose children meet the inclusion criteria will be provided a description of the study procedures and asked which aspects of the study they are willing to participate in. All families will be asked to complete three research assessments (pre-, mid-, and post-treatment) consisting of completing questionnaires and a short phone or video call. Families will be provided with a description of the three treatment options and informed that PCET is the default treatment option. They will then be asked if they are willing to be randomized to a treatment from two or three of the options. Randomization will be accomplished through a random number generator and will allow for a comparison of the relative effectiveness of each treatment by

controlling for other variables that might impact treatment outcome. The individual PCET is currently the standard treatment offered through the PADC and patients not interested in this treatment are not eligible for the study. When families are interested and eligible in participating in the clinical trial, the therapist or a study coordinator will obtain written consent and assent.

Families who decline to participate will have the PADC.

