Following the consent process, families who agreed to be randomized to a comparison treatment participate will be assigned to a treatment condition through random assignment. Families that did not agree to randomization will be scheduled in PCET (individual or intensive group depending on preference). The families will then be scheduled to begin therapy at the earliest date available. All enrolled families will complete the pre-treatment research assessment the day they begin treatment. The families will then begin treatment.

The mid-treatment evaluation will be completed after the sixth session for patients in the individual treatment conditions and six weeks after the start of treatment in the intensive group condition. After the mid-treatment assessment families in all conditions can receive any type of therapy interventions with their study therapist. The final assessment will be completed 14 weeks after the first session. All study assessments and individual treatment sessions will be recorded, unless participants opt-out of recording, to examine therapist fidelity. Families will record progress each week using a study form which will be gathered by therapists during visits and by therapists (or other study staff) via electronic message or telephone calls in the absence of inperson appointments.

Tests/Measures Administered

Table 2 Summarizes when study measures are completed, by whom and whether they are administered as part of clinical practice or as part of the research study.

Interviewer--administered measures: The interviewer measures will be administered by the practicing clinician at initial clinical interviewer and by study staff blind to the treatment condition at pre-, mid-, and post-tx.

(1) The MINI-Kids (Sheehan et al., 2010). This is a clinician-administered, structured interview that is currently administered as part of the PADC standard evaluation. Administered at clinical interview only.

(2) Pediatric Anxiety Rating Scale (*PARS; (Group, 2002).* The PARS is an interviewer administered scale consisting of five items assessing anxiety severity, frequency, distress, avoidance, and interference. The PARS has good psychometric properties (Group, 2002) and has been used as the primary continuous outcome measure in previous treatment studies (e.g., (Walkup et al., 2008).

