We anticipate that all patients will see minimal improvement in symptoms during the baseline period between the clinical evaluation and baseline pre-tx, and significant improvement from pret-tx to mid-tx and post-tx. In addition, we hypothesize that patients treated in the either PCET condition will demonstrate greater reductions in anxiety symptoms and impairment, as well as require fewer total treatment sessions, compared to patients in traditional CBT. To test this hypothesis, repeated-measures analyses of variance (which controls for baseline symptom severity) will be conducted to assess the change that occurs over time and between conditions. Because treatment changes after mid-treatment for some conditions, but not others, we will examine the changes at mid-treatment and post-treatment separately. The primary outcome variable will be change in symptom severity on a continuous variable as measured by the IE administered CGI-S. Secondary outcomes will be anxiety symptoms measured through parentreport (SCAS-P), child-report (SCAS-C), and clinician report (PARS). Dichotomous measures of improvement used in the literature will include receiving a score of 1 or 2 on the CGI-I, reduction on the PARS of 35% (response) and 50% (remission). Tertiary outcome variables will be impairment measured through the CSDS. Efficiency will be measured at the group level by number of treatment hours (included phone contacts) and symptom change effect size per hour of intervention. Number of dropouts vs. completers will be examined. Finally, we will examine treatment acceptability through the rate of drop-out and ratings of alliance. All statistical analyses will be conducted using intent-to-treat and completer analyses. Because patients that agree to each randomization option may differ in unmeasured ways, comparator analyses will be run in two ways. First, to avoid biasing the results by combining incompatible groups, we will include patients in comparisons only if they agreed to be randomized to each option (i.e., only patients that agreed to the possibility of being randomized to CBT will be included in the comparison between PCET-I and CBT). Second, to maximize power, we include all patients with randomization agreement as between subject variables. Exploratory analyses will include examining the relation to randomization choices and the moderating effects on outcome of diagnosis (OCD vs. anxiety disorder), symptom severity, age, medication use, etc.

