Power Statement: Based on the mean mid-tx CGI-S scores from the pilot study (PCET= 2.33, sd= .8; CBT = 3.17, sd =.8) and 14 patients are required per group to achieve 80% power to detect a difference between two groups at a p value of .05. Thus, the current proposed sample size of 20 participants be treatment conditions should be sufficient.

In regard to acceptability, we will assess the acceptability of each treatment to patients and their families. A between-groups analysis of variance will be conducted to assess for differences in the alliance and satisfaction of each treatment at posttreatment. Further, we will also conduct between-group mean comparisons of the number of drop outs.

Sample representativeness will be examined through group differences between patients that participated and those that declined through t-tests and chi-square analyses of symptom and demographic data collected at the clinical assessment.

Remuneration

Patients can earn up to \$50 for participation: up to \$25 for completing research assessments (\$5 for pre-treatment assessment and \$10 for each of the mid- and post-treatment assessments); up to \$25 for randomization: \$15 if they agree to the possibility of being randomized to one comparator and additional \$10 for agreeing to be randomized to the second comparator. All remuneration will be paid when the participant completes the study, and may be pro-rated based on completion of assessments. Patient remuneration will be payed from [name] research funds.

7. Possible Discomforts and Risks:

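### The stated 40 per condition is not ensured when families choose their own randomisation options, and the restricted CBT v PCET-5day comparison has no stated size

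*Combined protocol and SAP*

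**What the plan says.** Section 6, Participants, sets the size: "A total of 120 families (240 participants) (40 in each treatment condition". Under Procedures, families are asked whether they are "willing to be randomized to a treatment from two or three of the options", and "Randomization will be accomplished through a random number generator". Three statements fix which option sets can occur. Procedures makes families who do not want PCET-I ineligible, Design Justification lets families accept CBT, PCET-5day or both as comparator, and Remuneration pays separately for the first and second comparator. The sets are therefore PCET-I/CBT, PCET-I/PCET-5day, and all three.

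On families who decline randomisation: "Families that did not agree to randomization will be scheduled in PCET", in the individual or the group format as they prefer.

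The Statistical Plan runs each comparison in two ways. The first is restricted: "only patients that agreed to the possibility of being randomized to CBT will be included in the comparison between PCET-I and CBT". The second takes all patients, with randomisation agreement as a between-subject variable. The Power Statement uses pilot mid-treatment CGI-S values ("PCET= 2.33, sd= .8; CBT = 3.17, sd =.8") and concludes that "14 patients are required per group to achieve 80% power" "to detect a difference between two groups at a p value of .05". It sizes one two-group comparison and refers to 20 per condition. The abstract gives 60 in total.

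**The concern.** The number in each arm depends on what families choose, and the plan gives no expected choice rates. PCET-I can be filled from every set and from decliners, PCET-5day from two sets and from decliners, and CBT from two sets only. A single figure per condition therefore does not describe the sample that the design will yield.

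The figure that governs inference is the number randomised per contrast. For CBT v PCET-5day, the restricted rule leaves only families who accepted all three options. The protocol adopts that analysis to avoid combining incompatible groups, so its best-protected version of this part of Aim 4 is the one without a stated size. If few families accept all three, a null result there would be uninformative, and the plan gives no advance warning of it.

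**Working it through.** **Protocol's own figure.** Difference 3.17 − 2.33 = 0.84; SD 0.8; d = 0.84/0.8 = 1.05. With two-sided α = 0.05 (sidedness is not stated) and 80% power, the normal approximation gives n = 2(1.960 + 0.842)²/1.05² = 14.24 per group. The stated 14 is this value rounded down. The exact two-sample t-test gives 15.26, so 16; at 14 per group its power is 76%. The 14 is kept below as the protocol's own benchmark.

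**Arm sizes.** Let a = PCET-I/CBT families, b = PCET-I/PCET-5day families, c = three-option families and r = decliners, with a + b + c + r = 120. Assume equal allocation within sets. Expected numbers randomised:

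- PCET-I: a/2 + b/2 + c/3
- CBT: a/2 + c/3
- PCET-5day: b/2 + c/3

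PCET-I exceeds CBT by b/2 and exceeds PCET-5day by a/2. Forty randomised to each arm therefore needs r = 0, a = 0 and b = 0, which leaves c = 120.

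**Restricted contrasts.** CBT v PCET-5day has c/3 per arm. Setting c/3 = 14 gives c = 42, which is 42/120 = 35%, or 42/60 = 70%. PCET-I v CBT has a/2 + c/3 per arm.

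**Range over choice rates.** The documents give none, so all the mixes are assumptions. Power is for a two-sided t-test at d = 1.05, before dropout.

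| Decline / PCET-I+CBT / PCET-I+5day / all three (%) | CBT v 5day per arm, N = 120 (power) | PCET-I v CBT per arm, N = 120 | CBT v 5day per arm, N = 60 |
|---|---|---|---|
| 10/20/20/50 | 20 (90%) | 32 | 10 |
| 20/20/20/40 | 16 (82%) | 28 | 8 |
| 0/33/33/33 | 13.3 (73% at 13) | 33.3 | 6.7 |
| 25/25/25/25 | 10 (60%) | 25 | 5 |
| 40/20/20/20 | 8 (50%) | 20 | 4 |

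Power for PCET-I v CBT is 95% at 25 per arm, 99% at 33 and 90% at 20.

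**Chance imbalance.** Suppose the generator makes a simple draw with probability 1/3 for each arm. The chance that both CBT and PCET-5day reach 14 is then 23% with 42 three-option families, about 57% with 48 and 93% with 60 (multinomial). Blocking within that set would give 14/14/14 at 42. Blocking leaves c/3 unchanged.

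**The case against.** A reader might infer that the design cannot deliver 40 per condition. The documents do not support that. Participants does not say 40 randomised, and decliners may take PCET-5day. If 80 families choose PCET-I/CBT and 40 decline and all prefer PCET-5day, the arms are 40/40/40, though with no randomised CBT v PCET-5day contrast. Unequal allocation is not ruled out either.

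A reader might also infer that the randomisation is unstratified. The protocol is only silent: a random number generator is compatible with blocked lists per option set. Figure 1, to which Procedures refers, could not be read in the copy reviewed and may carry detail.

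Nor do the documents show that CBT v PCET-5day is underpowered as such. At 40% or more accepting all three, the restricted contrast has at least 16 per arm in expectation at 120 families. Remuneration pays an additional $10 for the second comparator, which pushes in that direction. With equal thirds, the shortfall is under one patient per arm (13.3 against 14). The all-patient analysis stays above 14 per arm at 120 families in every mix in the table, with 20 or more randomised to CBT and to PCET-5day.

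These limits stand. What they leave is the missing sizing. The all-patient analysis is only a partial answer, because it adds comparisons between option groups that were not randomised against each other and that the protocol itself suspects of unmeasured differences.

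**Conclusion.** The point holds as a gap in the stated size, not as proof of an unworkable design. Nothing in the plan ties randomisation within self-chosen sets to 40 per condition. Under equal allocation, 40 randomised to each arm is expected only if every family accepts all three options. The restricted CBT v PCET-5day contrast meets the protocol's 14 per group in expectation only with at least 42 three-option families. Below 35% acceptance at 120 families it falls short: 10 per arm and about 60% power at 25% acceptance.

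PCET-I v CBT, the contrast of Aims 2 and 3, is not threatened at 120 families: 25 to 33 per arm and power of 95% or more in the thirds and quarters mixes, and 20 per arm (90%) in the least favourable row.

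The power figures assume that the pilot d of 1.05, which Background attributes to the individual format, carries over to PCET-5day. They make no allowance for dropout, for clustering in groups of 4 to 8 families, or for any gain from baseline adjustment. The choice rates are assumptions throughout.

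**What to change.** 1. State the allocation ratio within each option set. Randomise with permuted blocks of varying size, concealed, from a separate list for each set (PCET-I/CBT, PCET-I/PCET-5day, all three). This removes chance imbalance but does not raise expected numbers.
2. Keep option set as a factor in the model, as the second analysis already does.
3. Replace the single per-condition figure with expected randomised numbers per contrast under stated option-set shares, and count decliners separately.
4. State that the restricted CBT v PCET-5day contrast meets the protocol's 14 per group only if at least 42 families accept all three options, before dropout.
5. Reconcile 120 families and 40 per condition with the abstract's 60 and the Power Statement's 20, because the share needed doubles from 35% to 70%.

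The cost is three lists instead of one and a less favourable stated size. No extra patients are needed.

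### In the two individual arms the mid-treatment assessment depends on reaching session six, so the mid-treatment intent-to-treat comparison is by default close to a completer analysis

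*Combined protocol and SAP*

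**What the plan says.** Under Procedures (section 6), families who accept randomisation "will be assigned to a treatment condition through random assignment" after consent, and therapy is booked after that. Every research assessment is then dated from treatment received:

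- Pre-treatment: "All enrolled families will complete the pre-treatment research assessment the day they begin treatment".
- Mid-treatment, individual PCET (PCET-I) and CBT: "The mid-treatment evaluation will be completed after the sixth session for patients in the individual treatment conditions".
- Mid-treatment, intensive group (PCET-5day): "six weeks after the start of treatment in the intensive group condition".
- Post-treatment, all arms: "The final assessment will be completed 14 weeks after the first session".

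Table 2 heads the mid-treatment column with both week and session six and does not say which applies to which arm. Procedures also says that every family is asked for all three research assessments, which are done by questionnaire and a brief call.

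The Statistical Plan says: "All statistical analyses will be conducted using intent-to-treat and completer analyses". The model is repeated-measures ANOVA and the primary outcome is change in CGI-S. Mid- and post-treatment are examined separately, because treatment changes after mid-treatment in some arms. On attrition it says: "Number of dropouts vs. completers will be examined". No method for missing scores is given, and nothing says whether a child who leaves treatment goes on being assessed. The Power Statement opens: "Based on the mean mid-tx CGI-S scores from the pilot study".

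**The concern.** An intent-to-treat comparison needs an outcome, or a principled way of handling its absence, for every child assigned. Here the mid-treatment score in two of the three arms is triggered by attendance. Children who stop early are the ones for whom intent-to-treat and completer results could differ, and they are the ones with no clearly scheduled score.

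Mid-treatment is also where the arms differ most by design. CBT withholds exposure for six sessions and then delivers it as in PCET, so the week-14 score cannot stand in for the missing one.

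If the children who stop are doing badly, leaving them out flatters their arm; if they stop because they have improved, it does the reverse. Unequal loss between arms would bias the contrast in a direction that cannot be known in advance. Because a started PCET-5day child is assessed by the calendar, the opportunity for loss also differs between the group arm and the individual arms.

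**Working it through.** **Step 1. Who has a scheduled assessment.** From Procedures and Table 2:

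| Randomised child | Pre | Mid | Post |
|---|---|---|---|
| Never starts, any arm | none | none | none |
| Starts PCET-I or CBT, stops before session six | start day | none clearly stated | week 14 |
| Starts PCET-5day, stops early | start day | week 6 | week 14 |
| Attends six sessions of PCET-I or CBT | start day | after session six | week 14 |

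The child in the first row has only the Time 0 CGI-S, rated by the practising clinician.

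**Step 2. What the named model does.** Conventional repeated-measures ANOVA uses children with a score at every time point in the model. With no imputation rule, the children in the first two rows fall out of the pre-to-mid comparison. In PCET-I and CBT, those who remain are essentially the children who attended six sessions.

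**Step 3. The plan's own sample size.** Inputs from the Power Statement: means 2.33 and 3.17, SD 0.8, 80% power, p = .05 (taken as two-sided).

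- Difference: 3.17 − 2.33 = 0.84.
- n per group = 2 × [0.8 × (1.960 + 0.842) / 0.84]² = 14.24. The stated figure is 14; rounding up gives 15, and a t-test calculation gives 16. The plan's figure is reproduced closely enough for this purpose.

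**Step 4. Is power the problem?** The documents give no dropout rate, so equal losses of 0, 10, 20 and 30% are assumed. The planned size is 20 per arm in the Power Statement and 40 per arm under Participants, so both are shown.

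| Planned per arm | Remaining | Power, normal approximation | Power, t-test |
|---|---|---|---|
| 20 | 20 / 18 / 16 / 14 | 91 / 88 / 84 / 79% | 90 / 86 / 82 / 76% |
| 40 | 40 / 36 / 32 / 28 | 97% or more throughout | 97% or more throughout |

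At 20 per arm, power stays above 80% up to a 20% loss. Power is not the main cost.

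**Step 5. Bias from omitted children.** If one of n children is omitted and would have scored g points above the mean m of the others, the full-arm mean is [(n − 1)m + (m + g)] / n = m + g/n. Omission therefore moves the mean by g/n. Take the pilot means as the observed means and assume that the omitted child would have scored 5:

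- One in PCET-I: (5 − 2.33)/20 = 0.13, or 16% of 0.84. At n = 40: 2.67/40 = 0.07.
- One in CBT: (5 − 3.17)/20 = 0.09. At n = 40: 1.83/40 = 0.05.
- One in each arm, n = 20: 0.1335 − 0.0915 = 0.04 net.
- Two in PCET-I and none in CBT, n = 20: the full PCET-I mean is (18 × 2.33 + 2 × 5)/20 = 2.597. The difference for all randomised is 3.17 − 2.597 = 0.57, against 0.84 analysed.

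These figures use raw mid-treatment scores. The primary outcome is change, and no baseline mean is given, so the gap on the change scale cannot be computed.

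**The case against.** The best reply is that the text is not closed. Table 2's column heading could be read as permitting a week-6 assessment, and all families are asked for three assessments with no attendance condition. That stands as an ambiguity. But the heading fits the arm-by-arm split in Procedures equally well and does not clearly give the individual arms a fallback. For the same reason, one cannot say for certain that every observed mid-treatment score in those arms will come from a child who attended six sessions.

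A reader might infer that the intent-to-treat analysis loses these children altogether. The documents do not support that. A child who attended session 1 keeps a calendar-based assessment at week 14, and post-treatment is analysed separately. Loss at mid-treatment is also the default result of the named model, not a stated rule. An unstated imputation could keep the child in the analysis, although the score would still be unobserved.

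A reader might also see here a safety gap concerning children redirected to other care after randomisation, calling for a suicidality check at session 1. The documents barely describe such a pathway. Suicidality and need for higher care are intake exclusions, and the Patient Safety statement in section 7 that high-risk children will be excluded can be read as restating eligibility. Ordinary dropout is the relevant case, and a safety check would recover no missing score.

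Two features soften the problem. Families choose which comparators they will accept before assignment, which should limit refusal. Weekly 0–10 severity ratings are collected by message or telephone when there is no visit, and these could inform a missing score. They are not CGI-S and are not blinded ratings.

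**Conclusion.** The point holds in a limited form and is minor. An individual-arm child who stops before session six has no clearly scheduled mid-treatment CGI-S, and a randomised child who never starts has no scheduled research assessment. Under the stated model, this makes the mid-treatment intent-to-treat comparison close to a completer comparison. The post-treatment analysis need not lose children who started.

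How much this matters is unknown. The number of early stoppers, their scores and the split between arms are all assumptions. A single omitted child has a small effect, and similar losses in both arms nearly cancel. Only unequal loss of children who differ markedly from the rest of their arm would distort the contrast materially.

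**What to change.** 1. Add a fallback date. For any randomised child who has not reached session six by six weeks after the booked first session, because the child never started or has stopped, do the mid-treatment assessment then, by questionnaire and phone or video call. Do the post-treatment assessment 14 weeks after that same booked date. State that children who leave study treatment continue to be assessed. Children who attend keep the current timing.
2. Define intent-to-treat as all randomised children. Replace repeated-measures ANOVA with a likelihood-based mixed model that uses all available scores. If Time 0 CGI-S is included, note that it comes from the practising clinician and not from the blinded assessor. Report missing mid-treatment scores by arm, and keep the completer analysis as secondary.

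This needs a protocol amendment, a few extra calls, and at most $25 per affected child at the existing rates ($5 + $10 + $10). Some families who leave will decline, so missing scores will be reduced but not eliminated. Scores taken after leaving reflect the assigned arm plus any other care received, and the report should say so. Mid-treatment timing will also differ somewhat between attenders and those assessed at the fallback date.

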- 1. *Examine the effectiveness of PCET through baseline comparisons*. All families in the Pediatric Anxiety Disorders Clinic (PADC) complete clinical assessments during the initial evaluation. All families eligible for anxiety treatment within the PADC will be invited to complete research assessments immediately prior to treatment, mid-treatment, and post treatment. This data will be used for a baseline-controlled evaluation of treatment effectiveness, i.e. symptoms change from clinical assessment to pre-assessment will be compared with change from pre-treatment to post-treatment.
- 2. *Comparative effectiveness of individual PCET and individual standard CBT*. The relative effectiveness of individual PCET and standard CBT will be examined through symptom change from pre-treatment to mid-treatment and post-treatment.
- 3. *Comparative efficiency of individual PCET and individual standard CBT*. The relative efficiency of individual PCET and standard CBT will be examined through the total number of sessions that patients attend over the 14 weeks of the study.
- 4. *Comparative effectiveness of group intensive PCET, individual PCET, and individual standard CBT*. The relative effectiveness of group intensive PCET versus individual PCET and standard CBT will be examined through symptom change from pre-treatment to mid-treatment and post-treatment.
- 5. *Acceptability*. The acceptability of the treatments will be examined through parent and child ratings of therapist alliance and satisfaction with services.

6. Research Plan:

Recruitment. The Pediatric Anxiety Disorder Clinic (PADC) receives referrals and provides treatment services to children with anxiety disorders. Families who come to the PADC for outpatient services will receive a verbal description of the clinical trial at their initial appointment. This description will be provided by the clinician conducting their evaluation.

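### The repeated-measures ANOVA is said to control for baseline severity, but as described it compares unadjusted change in CGI-S; precision is lost and the power statement rests on a different quantity

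*Combined protocol and SAP*

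**What the plan says.** The Statistical Plan (section 6) states that "repeated-measures analyses of variance (which controls for baseline symptom severity) will be conducted to assess the change that occurs over time and between conditions". It gives no model terms. The only extra between-subject term it mentions is agreement to randomisation, in the second of two comparator analyses. Symptom severity otherwise appears only as an exploratory moderator.

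Three statements fix what is compared:
- Aim 2 (section 5): "The relative effectiveness of individual PCET and standard CBT will be examined through symptom change from pre-treatment to mid-treatment and post-treatment".
- Statistical Plan, outcome: "The primary outcome variable will be change in symptom severity on a continuous variable as measured by the IE administered CGI-S".
- Statistical Plan, timing: "Because treatment changes after mid-treatment for some conditions, but not others, we will examine the changes at mid-treatment and post-treatment separately".

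The Power Statement starts from pilot values: "Based on the mean mid-tx CGI-S scores from the pilot study (PCET= 2.33, sd= .8; CBT = 3.17, sd =.8". It concludes that "14 patients are required per group to achieve 80% power to detect a difference between two groups at a p value of .05" and takes 20 per condition as sufficient. It gives no baseline SD, change-score SD or correlation between visits. The Participants paragraph gives 40 per condition.

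**The concern.** A reader of the bracketed phrase will believe that baseline imbalance in CGI-S has been dealt with. Putting the pre-treatment score in as one level of a repeated factor does not do that. It subtracts the score, whereas conditioning would use the regression of the later score on the earlier one. An analyst could therefore run either change scores or a covariate-adjusted model and claim to have followed the plan, and on one dataset the two can give different estimates and p-values for the primary outcome.

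At stake is the precision of the primary comparison and its sensitivity to chance imbalance, at a size (20 per arm in the Power Statement) where imbalance is a practical matter. The Procedures describe a random number generator and no stratification by severity. The power calculation also does not describe the analysis that would be run.

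**Working it through.** **Inputs.** From the Power Statement: means 2.33 and 3.17, so a difference of 3.17 − 2.33 = 0.84; mid-treatment SD .8; alpha .05; 20 per arm. From Participants: 40 per arm. Assumed, because the documents do not give them: two-sided testing, no dropout, the pre-to-mid correlation rho (.1 to .7), and the baseline SD (.8, .6 or .5).

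**1. The plan's own figure.** For raw mid-treatment scores by normal approximation, n = 2 × (1.96 + .8416)² × (.8/.84)² = 14.24 per group, consistent with the stated 14. A two-sample t-test needs 16. No baseline quantity enters.

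**2. What the group-by-time test is.** With two time points and two arms, the interaction contrast is the difference between arms in mean (mid − pre), and its F is the squared t on change scores. A check on simulated data gave 18.570 for both. With three arms (Aim 4) it equals a one-way ANOVA on change. If pre, mid and post sit in one model, the pre-to-mid contrast is still the difference in mean change.

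**3. What a chance imbalance does.** Given a baseline difference D between arms, the expected change estimate is the true effect + (rho × SD_mid/SD_base − 1) × D. With equal SDs the slope is rho − 1. The standard error of D at 20 per arm is .8 × √(2/20) = .253. A one-standard-error imbalance therefore moves the estimate by .7 × .253 = .18, .5 × .253 = .13 and .3 × .253 = .08 points at rho .3, .5 and .7. At baseline SD .5 the shift is .08 and .03 at rho .3 and .5. The shift can go either way and is already part of the change-score variance. Under ANCOVA the slope is zero.

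**4. Power.**
- Change: Var = SD_base² + .8² − 2 × rho × SD_base × .8; noncentral t with 2n − 2 df.
- ANCOVA, baseline only: residual SD .8 × √(1 − rho²); 2n − 3 df; power averaged over the chance baseline imbalance. It does not depend on the baseline SD.

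Example at rho .3, equal SDs, 20 per arm. Change SD = √(.64 + .64 − .384) = .947; SE = .947 × √.1 = .299; .84/.299 = 2.81; power 78%. The ANCOVA residual SD = .8 × √.91 = .763; power 92%.

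| 20 per arm | rho .1 | .3 | .5 | .7 |
|---|---|---|---|---|
| Change, baseline SD .8 | 67% | 78% | 90% | 98.7% |
| Change, baseline SD .6 | 78% | 87% | 95% | 99.5% |
| Change, baseline SD .5 | 82% | 89% | 96% | 99.5% |
| ANCOVA, any baseline SD | 89% | 92% | 96% | 99.4% |

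Raw mid-treatment scores give 90% at 20 per arm, which equals the change analysis only at rho .5 with equal SDs. With equal SDs, change-score power falls below 80% only when rho is under about .33. For 80% power with equal SDs, the change analysis needs 27/21/16/10 per arm and ANCOVA 16/15/13/9.

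At 40 per arm with equal SDs, change-score power is 90.6% at rho 0 and rises with rho.

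**The case against.** Change from pre-treatment is a legitimate, prespecified estimand, and preferring ANCOVA is a recommendation about efficiency. The weak power cases need 20 per arm, a low correlation and a baseline SD near .8 together. Eligibility narrows baseline severity from both ends: a primary anxiety diagnosis suited to weekly outpatient therapy, and exclusion of cases needing a higher level of care. A baseline SD below .8 is therefore plausible, though not shown, and the same narrowing could lower rho. All of this stands and limits the size of the point. It does not make the bracketed phrase accurate.

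The figure of 14 does not by itself prove a raw-score calculation. With equal SDs the change analysis needs 16 per group at rho .5 and 13 at rho .6, so some value between would also give 14. The inference rests on the Power Statement citing mid-treatment means and SDs and nothing else.

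A reader might infer more than the documents support:
- That the planned test is biased or has the wrong error rate. Under randomisation it is unbiased, and simulated type I error was 4.9 to 5.1%.
- That the trial is underpowered. Change-score power is below 80% only in one corner of the assumed range at 20 per arm, and not at 40 per arm.
- That the 14 is wrong. It is reproduced by normal approximation to within rounding.
- That ANCOVA was intended, so nothing needs changing. That may be so, but the plan does not say it, and the wording would need the same repair.

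**Conclusion.** The point holds as one of wording and precision, and should be fixed before the data are analysed. On the natural reading the primary test compares unadjusted change, so the statement about baseline control is inaccurate, and the power basis matches that test only near rho .5 with equal SDs.

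At 20 per arm with equal SDs, conditioning on baseline adds about 22, 14, 6 and under 1 percentage points of power at rho .1, .3, .5 and .7. With a baseline SD of .5 it adds about 7 and 2 points at .1 and .3 and nothing from .5 upward. These sizes rest on the assumed rho and baseline SD, two-sided testing, no dropout and full inclusion of each arm. Neither bias nor inadequate power is established.

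**What to change.** For each pairwise randomised comparison, analyse mid-treatment and post-treatment CGI-S in two separate ANCOVAs with pre-treatment CGI-S as covariate. This keeps the separate examinations already planned. Name the pre-treatment research rating explicitly, because the plan also uses the word baseline for the waiting period after the clinical evaluation. Replace the bracketed phrase with this statement, and restate the Power Statement for this analysis over a stated range of rho.

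A term for the randomisation option set is optional, and only for the two comparisons that involve individual PCET. The Procedures say of families: "They will then be asked if they are willing to be randomized to a treatment from two or three of the options". Individual PCET is in every set, because families not interested in it are ineligible, and CBT and PCET-5day are the optional comparators. The first comparator analysis says: "we will include patients in comparisons only if they agreed to be randomized to each option". CBT versus PCET-5day then contains only families who accepted all three options, so the term is constant there and must be left out.

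The cost is plan wording and a re-run power calculation. Pre-treatment CGI-S is already collected by staff blind to condition (Table 2; Tests/Measures Administered), so no data or visits are added. The model spends one degree of freedom. The power loss is well under 1 percentage point if the baseline SD is small and rho is .5 or more.
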